Principal research questions/objectives include: 1. Investigate potential differences in ASCs induced by a single session of HVB—in particular Conscious Connected Breathing (CCB)—versus a body scan meditation. 2. Examine whether HVB (CCB) induces ASCs comparable to psychedelics (via the Altered States Database, an open-science project based on systematic literature reviews). 3. Investigate potential differences on mental health and wellbeing after HVB or a body scan meditation. 4. Examine correlation between ASCs and changes on mental health and wellbeing, in addition to the relationship between preparedness/predictiveness of participants to experience psychedelic effects and ASCs.

Materials/Methods

Unlike slow breathwork, high ventilation breathwork (HVB) has not been exposed to the same level of robust clinical testing to date [2,6-8], a necessary step to realise its potential application as a therapeutic modality. We will conduct the first randomised-controlled trial (RCT) of HVB on altered states of consciousness (ASCs). This will take the form of a small pilot study wherein participants are randomised to in-person, guided HVB or a meditation group.

Study type

This will be an experimental study, where participants are randomly assigned to a HVB intervention or body scan meditation. This will be a small-scale pilot RCT, hopefully leading to a large-scale clinical trial in the future (depending on funding).

Data collection procedures

Quantitative data: The primary outcomes will be ASCs as measured by the Five Dimension ASC Rating Scale (5D-ASC) [9], the short Mystical Experience Questionnaire (MEQ) [10], and Emotional Breakthrough Inventory (EBI) [11].

Secondary outcomes include: the Psychological Insight Questionnaire (PIQ) [12], Depression Anxiety Stress Scales (DASS) [13], Short Warwick-Edinburgh Mental Wellbeing Scale (SWEMWBS) [14], Imperial Psychedelic Predictor Scale (IPPS) [15], PROMIS Sleep-Related Impairment Scale (PROMIS-4a) [16], Shortened Fatigue Questionnaire (SFQ) [17], and Cambridge Depersonalisation Scale-State Version (CDSS) [18].

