There will also be optional open-ended responses on overall experience of the meditation or breathwork. The following state measures will be completed immediately after the HVB and meditation sessions: 5D-ASC, MEQ, EBI and CDSS. The following trait measures will be completed 7-10 days before and 7-10 days after the breathwork and meditation sessions: DASS, SWEMWBS, PROMIS and SFQ. The IPPS will be completed when subjects consent to participating, and the PIQ will be completed 7-10 days after the breathwork and meditation sessions.

Qualitative data: Optional open-ended responses will capture participants' lived experiences after the breathwork and meditation sessions.

Sample

Given this is a small pilot study, 24 participants (12 per group) will be recruited. The studies of Bahi et al. (2023) and Havenith et al. (2024) report HVB having comparable effects on ASCs to moderate-high doses of psilocybin, which has large-very large effect sizes on ASCs. This is an ethical number of participants for a single session HVB intervention with two breathwork facilitators present. It is ideal to have no more than six breathworkers per facilitator.

Accordingly, there will be two groups of 12 for our study (12 in the HVB group, and 12 in the meditation group). At 80% power with an alpha of 0.05, based on Havenith et al.'s HVB study's between-groups effect size (1.29) on the self-completion depressive symptomology survey, a sample size of 22 is needed, allowing room for potential attrition. Effect sizes reported by Bahi et al. were greater, but this was a within-groups design.

Participants will be recruited from the local area using advertisements online (social media/email) via the PI and (co)facilitators' networks. It will be incumbent upon those people interested in taking part to contact the PI. Participants will be comprehensively screened and the inclusion criteria will be adults with experience of HVB, living in Brighton (UK) and the surrounding area. Given the nature of HVB, the comprehensive eligibility criteria are as follows:

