Participants will be briefly screened for eligibility prior to taking part into the study. They will be randomly allocated to HVB or meditation groups using block randomisation (1:1), stratified by scores on the brief 9-item Imperial Psychedelic Predictor Scale (IPPS), which will be completed shortly after the Consent Form has been signed. Short self-completion questionnaires will be administered to participants ~1 week pre and post the HVB or body scan meditation, along with once immediately after the HVB and meditation. The platform used for questionnaires will be Qualtrics and, where visual analogue scales are used, will contain a scale with 0 (%) on the left and 100 (%) on the right. The single sessions of breathwork and meditation will take place at Little Dippers in Brighton, a naturalistic setting where the facilitator regularly teaches HVB.

Participants will be compensated 5GBP, 10GBP and 15GBP (money) per questionnaire completed (30GBP total but in a phased manner to increase retention). Moreover, participants, regardless of group, will be participating in an active intervention (HVB or body scan meditation) which will be provided free of charge.

Processing and Analysis Plan

Results will be analysed using the software programme *R*. The outcome measures collected on the day of the HVB or meditation will be analysed using simple quantitative analyses (i.e., unpaired t-test or Mann-Whitney U-test depending on distribution of the data), whilst the outcomes ~1-week pre-post will be analysed using repeated-measure analysis of variance (ANOVA) or Friedman's test depending on distribution of the data. Changes on the mental health and wellbeing measures will be correlated with scores on the ASC measures. Simple qualitative content analysis will be used to analyse any responses to open-ended questions of participants' experience of the HVB or meditation.

Ethical considerations

The Brighton and Sussex Medical School Research Governance and Ethics Committee (RGEC) has assessed this project and granted Ethical and Research Governance Approval to proceed (Reference Number: ERA/GF221/9/1).

References

1. Havenith, M. N., Leidenberger, M., Brasanac, J., Corvacho, M., Carmo Figueiredo, I., Schwarz, L., ... & Jungaberle, A. (2025). Decreased CO₂ saturation during circular breathwork supports emergence of altered states of consciousness. *Communications Psychology*, 3(1), 59.

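### Does the unstated number of group sessions per arm undermine the planned comparison of HVB with meditation?

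*Combined protocol and SAP*

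**What the plan says.** The Sample section of the combined protocol and SAP justifies the size partly on delivery: "This is an ethical number of participants for a single session HVB intervention with two breathwork facilitators present". It adds "It is ideal to have no more than six breathworkers per facilitator" and concludes "Accordingly, there will be two groups of 12 for our study (12 in the HVB group, and 12 in the meditation group". The Materials/Methods section says that "participants are randomised to in-person, guided HVB or a meditation group". Under Procedure, "They will be randomly allocated to HVB or meditation groups using block randomisation (1:1"), with stratification by the IPPS score, and "The single sessions of breathwork and meditation will take place at" one named venue in Brighton. The Abstract has one facilitator leading in both arms.

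The first objective under Research Aims/Questions is "Investigate potential differences in ASCs induced by a single session of HVB" compared with a body scan meditation, and the Summary likewise sets one guided session of each kind against the other. Under Processing and Analysis Plan, outcomes collected on the day "will be analysed using simple quantitative analyses (i.e., unpaired t-test or Mann-Whitney U-test depending on distribution of the data"). No number or date of sittings is given, and group delivery is not mentioned in the analysis.

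**The concern.** Two facilitators with at most six breathworkers each make 12, which is the size of the HVB arm. Together with the wording on single sessions, this suggests that each arm meets once, as a group. Everything particular to that sitting (the date, the mood of the group, the delivery on the day) would then be part of the estimated arm effect. The three primary outcomes (5D-ASC, MEQ, EBI) are completed straight after the session, so they are directly exposed to it.

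The Abstract and the research aims also speak of HVB and meditation as methods. A reader who takes the p-value as evidence about the methods, over all sessions that might have been held, is treating 12 people in one room as 12 independent samples of the method. If sessions differ, that p-value is too small and the interval too narrow. At stake is whether a significant primary result would be credited to HVB when part of it came from one particular sitting.

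**Working it through.** **The plan's own figure.** Inputs from the Sample section: effect size 1.29, alpha 0.05 (taken as two-sided), power 80%, required total 22. A two-sample t-test with the noncentral t distribution gives power of 77.9% with 10 per arm and 82.1% with 11 per arm, so the total of 22 is reproduced. The planned 12 per arm gives 85.5%. These figures assume independent observations.

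**How many sittings?** The documents do not say. One of 12 per arm is the natural reading for HVB. It is weaker for meditation, because the six-per-facilitator ratio concerns breathworkers. A single session can also mean one session per participant.

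**Size if there is one sitting per arm and the result is generalised to all sessions.** Let m = 12 be the number per sitting and rho the intra-session correlation. The documents give no rho, so the values below are assumptions. Under the null hypothesis the t statistic is a t variable on 22 degrees of freedom multiplied by f = sqrt((1 + 11 rho)/(1 - rho)). The critical value is 2.074.

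- Type I error = 2 P(t22 > 2.074/f).
- Half-width of the 95% interval, in within-session SDs = 2.074 × f × sqrt(2/12) = 0.847 f.

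| rho | f | Type I error | Half-width | Interval around 1.29 |
|---|---|---|---|---|
| 0 | 1.000 | 5.0% | 0.847 | 0.44 to 2.14 |
| 0.02 | 1.116 | 7.65% | 0.945 | 0.35 to 2.23 |
| 0.05 | 1.277 | 11.87% | 1.081 | 0.21 to 2.37 |
| 0.10 | 1.528 | 18.83% | 1.293 | 0.00 to 2.58 |

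At rho = 0.01 the type I error is 6.3%. The lower limit at rho = 0.10 is -0.003. It depends on the unit: if the difference and the half-width are both in total SDs, the half-width is 0.847 × sqrt(2.1) = 1.23 and the lower limit is 1.29 - 1.23 = 0.06. The value 1.29 comes from a depression survey, not from a primary outcome.

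**What could the analysis do about it?**

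- One sitting per arm: between-session degrees of freedom = 2 sittings - 2 arms = 0. No session term can be fitted, and the data carry no information about rho.
- Two sittings of six per arm: the unadjusted type I error falls to about 6.1%, 7.9% and 11.2% at rho = 0.02, 0.05 and 0.10 (simulated). There are 4 - 2 = 2 between-session degrees of freedom, with a critical value of 4.303. A test on session means then has power of about 40%, 36% and 31% at rho = 0.01, 0.05 and 0.10 for an effect of 1.29, against 85.5% for the planned test under independence.

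**Which contrast does the plan test?** Individuals are randomised. A shared session effect is the same for everyone in an arm, so it shifts the arm mean and leaves the within-arm scatter unchanged. The unpaired test therefore keeps its level for the difference between the two sessions as delivered, whatever rho is. The figures above rho = 0 arise only when the target is widened to a population of sessions, which the plan does not define.

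**The case for a change.** The strongest case for a change is that the wider reading is foreseeable. The Abstract states the aim in terms of HVB and meditation, results are to be set beside psychedelic data through the Altered States Database, and the trial runs tests justified by a power calculation. Calling the study a small pilot is a general caution and says nothing about sessions. Sharing a facilitator and a venue removes two sources of difference between sittings, but not the date or the group dynamics. Stating the count and limiting the conclusion in advance would take two or three sentences, and a table of intervals over assumed correlations would take a few lines of R.

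Much of this stands. If there is one sitting per arm, the aliasing is real, and claims about the methods need a caveat when the results are discussed. What does not stand is that the plan must change to achieve it. Writing down the count or the caveat alters no estimate, interval or test, and removes no bias. The table would multiply each interval by 1.12, 1.28 and 1.53 whatever the data show. It rests on correlations that nothing in the documents supports, would be only approximate if the Mann-Whitney test is used, and leaves the confounding in place. Statisticians could reasonably disagree about its value, and printing chosen correlations could give them an authority they lack.

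**Conclusion.** No change to the plan follows. The number of sittings is an omitted detail that the study team will know and can give when reporting, together with the ordinary limitation that applies if there was one per arm. The planned t-test or Mann-Whitney test is valid for comparing the two sessions as delivered, which is the comparison in the Summary and in the first research objective.

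The possible inflation, from 5% to between 7.65% and 18.83%, requires three things together: one sitting of 12 per arm (likely but unstated), an intra-session correlation of 0.02 to 0.10 (assumed), and a conclusion drawn about all sessions. Even then, a difference as large as the planning value of 1.29 keeps its interval above zero at 0.02 and 0.05 and is borderline only at 0.10. With 24 participants and at most six breathworkers per facilitator, delivery in few sittings is a fair trade-off for a pilot. Only several sittings per arm in the larger trial that the plan hopes for would separate session from method.

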Breathing is fundamental to life, rooted in the Latin word "spiritus," meaning spirit or life force. Through this project, we aim to explore the impact of high ventilation breathwork (HVB), a practice that uses deliberate, intensified breathing to create altered states of consciousness (ASCs). These states have been described as lived experiences that expand perception, foster a sense of connection, and bring deep personal insights. While substances like psychedelics are known to induce ASCs, they are often restricted due to costs, legal limitations, and health concerns. HVB, however, offers an accessible, drug-free way to reach similar states. Early research even suggests that HVB can lead to experiences comparable to those produced by medium-to-high doses of certain psychedelics, like psilocybin. Yet, unlike meditation or other therapeutic practices, HVB has not been rigorously studied in clinical trials. Our study plans to take an important first step by conducting a randomised controlled trial (RCT) on the effects of a single guided HVB session. This will involve experienced breathwork practitioners and will assess a range of outcomes, including ASCs, mystical experiences, emotional breakthroughs, and overall mental wellbeing. To help us understand the unique effects of HVB, we will also have a comparison group, where participants will engage in a meditation session led by the same facilitator. Essentially, we will be comparing a single guided session of HVB (intervention) to a single guided session of body scan meditation (active comparator). Then, using the Altered States Database, an open-science project based on systematic literature reviews, we can compare to prior data on altered state-induction methods like meditation and psychedelics. The primary aim is the impact of HVB and meditation on ASCs. Secondary aims relate to mental health and wellbeing. For the first time we will also examine the relationship between predictiveness of the psychedelic experiences emerging from HVB and meditation. By conducting this study, we hope to create a foundation for future clinical research and build evidence on HVB's potential as a therapeutic tool. This project responds to the growing interest in non-drug methods for achieving profound mental and emotional states—showing that the key to these transformative experiences may be as close as our own breath.

Introduction

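### Randomisation is stratified by IPPS, but the session-day tests ignore it; if IPPS is prognostic those tests are conservative, and adjusting costs almost nothing

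*Combined protocol and SAP*

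**What the plan says.** - **Allocation (Procedure):** "block randomisation (1:1), stratified by scores on the brief 9-item Imperial Psychedelic Predictor Scale (IPPS". The number of strata, cut-points and block size are not given.
- **Timing (Data collection procedures):** "The IPPS will be completed when subjects consent to participating". Because allocation uses the score, IPPS is a true baseline variable.
- **Session-day analysis (Processing and Analysis Plan):** "unpaired t-test or Mann-Whitney U-test depending on distribution of the data". This covers the measures completed straight after the session: the three primary outcomes (5D-ASC, MEQ, EBI) and the secondary outcome CDSS. No covariate is named for any comparison of the arms.
- **Role of IPPS:** Research Aims/Questions includes examining "the relationship between preparedness/predictiveness of participants to experience psychedelic effects and ASCs". The relationship is posed as a question, no correlation is stated, and the analysis plan names no method for it. Data collection procedures also lists IPPS among the secondary outcomes.
- **Sample size (Sample):** 12 per arm are to be recruited. For an effect of 1.29, 80% power and alpha 0.05, "a sample size of 22 is needed, allowing room for potential attrition".

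**The concern.** Stratifying on a baseline score makes sense mainly if the score is thought to predict outcome. If it does, balancing the arms on it removes part of its variance from the true error of the arm difference. An unadjusted two-sample test still counts that variance in its standard error, so the test rejects too rarely under the null and its confidence intervals are too wide.

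The design would then have gained precision that the analysis discards. With 12 per arm that can matter. The planning effect of 1.29 also comes from a depressive-symptom survey and not from a session-day primary outcome, so the true effects on the primaries could be smaller.

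**Working it through.** **Inputs from the documents.** 12 per arm, or 11 per arm if only 22 complete; alpha 0.05; d = 1.29; allocation stratified by IPPS; unadjusted test.

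**Assumptions, not in the documents.** Two-sided test; two strata split at the median with 6/6 allocation in each; IPPS and outcome normal with unit variance; complete data; the same IPPS slope in both arms unless stated; r from 0 to 0.5; d = 1.0 as an example of an effect below the planning value.

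**1. The plan's own sample size.** For a two-sample t-test the noncentrality is d√(n/2).
- n = 10 per arm: 1.29 × √5 = 2.885, power 77.9%.
- n = 11 per arm: 1.29 × √5.5 = 3.025, power 82%.
- n = 12 per arm: 1.29 × √6 = 3.160, power 85.5%.

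So 22 in total is reproduced.

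**2. Size of the standard-error mismatch at r = 0.5.** A median split captures 2/π = 0.637 of the variance of a normal score.
- Nominal SE used by the t-test: √(2/12) = 0.408.
- True SD of the arm difference: √[(2/12)(1 − 0.25 × 0.637)] = √(0.1667 × 0.841) = 0.374.
- SE with continuous IPPS in the model: √[(2/12)(1 − 0.25)] = 0.354.

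Simulation gives 0.405, 0.373 and 0.352. The t-test SE is therefore too large by 0.405/0.373 = 1.086, about 9%.

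**3. Simulated type I error and power at d = 1.0, 12 per arm** (40,000 trials per scenario; t-test on 22 df, ANCOVA on 21 df).

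| r (both arms) | t-test type I error | t-test power | ANCOVA power |
|---|---|---|---|
| 0 | 4.9% | 0.65 | 0.64 |
| 0.2 | 4.7% | 0.65 | 0.66 |
| 0.3 | 4.5% | 0.65 | 0.68 |
| 0.5 | 3.3% | 0.66 | 0.77 |

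ANCOVA type I error is 4.9–5.1% throughout. With 1:1 allocation that is not stratified, the t-test stays near 5%, so the conservatism comes from stratifying and then leaving the stratifier out.

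**4. Planning effect, d = 1.29, 12 per arm (t-test, then ANCOVA).**
- r = 0: 85.5%, 84.7%.
- r = 0.2: 86.1%, 86.5%.
- r = 0.3: 86.0%, 87.8%.
- r = 0.5: 87.2%, 93.2%.

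With 22 completers the t-test has 0.82–0.83.

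**5. Sensitivity.**
- IPPS predictive only under breathwork, d = 1.0: 0.65 to 0.67 if r = 0.5 in that arm; no gain if r = 0.3 (0.65 and 0.65).
- Three strata, r = 0.5, d = 1.0: 0.66 to 0.77.
- 11 per arm, d = 1.0: 0.62 to 0.72 at r = 0.5; 0.61 to 0.60 at r = 0.
- Fixed cut-point with permuted blocks of 2 or 4, some incomplete: t-test type I error 4.4–4.5% at r = 0.3 and 3.4% at r = 0.5, the same pattern.

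**6. Non-normal branch** (exponential residuals, d = 1.0). Mann-Whitney (20,000 trials) against ANCOVA on ranks with 499 permutations within strata (4,000 trials):
- r = 0: 0.80 to 0.81.
- r = 0.3: 0.78 to 0.81.
- r = 0.5: 0.74 to 0.84.
- r = 0.5 under breathwork only: 0.77 to 0.80.

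Type I error of the rank method was 4.8–5.6%. The Monte Carlo standard error at 4,000 trials is √(0.8 × 0.2/4,000) = 0.006, so the one-point difference at r = 0 is noise.

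**The case against.** The strongest reply is that nothing here is wrong. The planned test is valid, the estimate is unbiased, and the trial is a small pilot that deliberately uses simple tests. The benefit depends on a correlation that the documents leave open. It is large only if IPPS predicts about equally well under breathwork and under a body scan, at r near 0.5. At r of 0.2, or with prediction confined to the breathwork arm, the gain is 0 to 2 points. The 11-point figure uses d = 1.0, which is not in the documents; at the planning effect the gain at r = 0.5 is 93.2 − 87.2 = 6 points.

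All of that stands, and it limits the point to a minor one. It is also fair that IPPS is not unused: the aims relate it to ASCs. What is missing is IPPS in the comparison of the arms. Finally, a rank analysis that permutes within strata needs those strata recorded, and a switch to ranks needs a criterion, which the plan's own switch also lacks.

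The reply does not remove the asymmetry. The worst case for adjusting is about 1 point of power, and the best case run is about 11.

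**Conclusion.** The concern holds as a minor, conditional efficiency point. If IPPS is prognostic, the unadjusted session-day tests are conservative: at r = 0.5 in both arms the true type I error is about 3.3% and the standard error 8–9% too large. ANCOVA then adds about 11 points of power at d = 1.0 and 6 at d = 1.29. At r of 0.2 or less the difference is negligible, and at r = 0 adjusting loses about 1 point. Bias and false-positive risk are not at issue, and the 80% target at d = 1.29 is met either way.

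These sizes rest on the assumed correlation, normal outcomes (except in the rank branch) and assumed strata. The combined procedure of checking residuals and then choosing a branch was not simulated.

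**What to change.** Replace the session-day analysis text with: *Each of 5D-ASC, MEQ, EBI (primary) and CDSS (secondary) will be compared between arms by ANCOVA with continuous IPPS score as covariate, reporting the adjusted mean difference and 95% CI. If residuals are clearly non-normal, the arm effect will be tested by ANCOVA on ranks of the outcome and of IPPS, with the p-value from permuting arm labels within the IPPS randomisation strata.*

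The same edit should state the IPPS cut-points, number of strata and block size, and say how non-normality will be judged. Ranks matter in the second branch: a permutation test built on means had 0.67 power against 0.80 for Mann-Whitney under skew at r = 0.

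The cost is a short change to the analysis plan and one degree of freedom, with no new data.

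A separate labelling correction, which carries no weight in the rating: list IPPS as a baseline and stratification variable instead of a secondary outcome, since a score taken before allocation cannot be an effect of treatment.

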Our Lab has started characterising phenomenological and neurophysiological effects of HVB to inform its mechanism of therapeutic action, safety profile and future application. Clinical observations and data from neurophysiological studies indicate that HVB is associated with extraordinary changes in subjective experience, and profound effects on central and autonomic nervous systems functions through modulation of neurometabolic parameters and interoceptive sensory systems [2]. Nondrug alternatives for eliciting and working with ASCs are needed, as many individuals wish to derive therapeutic benefit via experiencing psychedelics' effects without the need to ingest substances. Breathing provides a potential resource that we have at our disposal (here and now) for improving wellbeing, and its consciousness expanding effects can be stopped at any point by simply returning to a normal cadence. With HVB we are not solely relying on an external source in the form of a drug compound, but our own innate inner capacity for healing. However, like psychedelics, as HVB becomes increasingly popular, it is extremely important that the hype is grounded in—and calibrated with—robust research evidence. This translates to rigorous clinical testing.

The study is a randomised controlled trial (RCT) involving up to 24 healthy adult participants who have prior experience with HVB. Participants will be randomly allocated to either the HVB or meditation group. The study will assess outcomes such as ASCs, mystical experiences, emotional breakthroughs, psychological insight, and overall wellbeing.

Motivation

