Inclusion Criteria: Healthy adults (18-65) in Brighton and the surrounding area; Prior experience practising high ventilation breathwork in the form of conscious connected breathing; No history of adverse events during such prior breathwork sessions. *Exclusion Criteria:* History of hypotension; Hypertension; Respiratory or cardiovascular problems; Fainting or syncope; Epilepsy or seizures; Panic disorder or panic attacks; Cerebral aneurysm; Pregnancy (and possibility one might be pregnant, trying to get pregnant, or are breastfeeding); Breathlessness; Bradypnea; Tachypnoea; Any mental/physical issues affecting the ability to engage in breath control activities.

Procedure

Prospective participants will be emailed an Information Sheet—and they will be given as long as needed to decide if they wish to participate. A Consent Form will be completed prior to any study related procedure. The informed consent process will include aims, rationale, methods and potential adverse effects of the study and will be followed by the completion of the Consent Form. The participant will be allowed as much time as they wish to consider the information, and the opportunity to question the PI, their GP, or any other independent parties to decide whether they will participate in the study. The PI taking consent will explain to the potential participants that they are free to refuse any involvement within the study or alternatively withdraw their consent at any point during the study—for any reason. The informed consent of the participant will be recorded and retained using an online form, with a copy of the signed Consent Form of which they can keep. No study procedure will be carried out until informed consent has been obtained from the participant.

Participants will be able to withdraw from the study at any time, and for any reason, without having to provide any explanation for their decision. Participants will be told that they can withdraw from the study at any time. If they request it, their data can be removed from the database. The deadline for the withdrawal of their data will be at the time of completion of data analysis. We expect this to be around 3 months after the session.

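### Block randomisation by IPPS score states no strata, block size, concealment or timing; if done one by one it often misses 12 per group, which a closed-list paired draw would avoid

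*Combined protocol and SAP*

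**What the plan says.** The Procedure section specifies "block randomisation (1:1), stratified by scores on the brief 9-item Imperial Psychedelic Predictor Scale (IPPS", with the scale filled in soon after consent. The Sample section sets the size: "24 participants (12 per group) will be recruited", and later "two groups of 12 for our study (12 in the HVB group, and 12 in the meditation group". It ties that number to session capacity, describing "a single session HVB intervention with two breathwork facilitators present" and adding: "It is ideal to have no more than six breathworkers per facilitator". The Introduction is looser, with "up to 24 healthy adult participants who have prior experience with HVB".

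Enquiries go to the PI (Sample) and the PI takes consent (Procedure). Eligibility screening is described without naming who does it. One exclusion is a matter of judgement: "Any mental/physical issues affecting the ability to engage in breath control activities".

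The documents do not give the number of IPPS strata or their cut-points, the block size, who makes or holds the list, how allocation is concealed, or whether participants are allocated as they arrive or in one batch.

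**The concern.** Blocking within strata equalises the arms only where blocks are filled. With 24 people spread over two or more IPPS strata, each stratum can stop mid-block, and the leftovers can add up in the same direction. The stated arm sizes are then missed, and an HVB session above 12 departs from the plan's own preferred facilitator ratio.

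The second issue is foreseeability. Arms cannot be hidden from participants or facilitators once sessions are assigned. With small blocks, anyone who can see earlier assignments and knows the block size and stratum can sometimes deduce the next arm. If that person also had a say in a judgement-based exclusion, who enters an arm could come to depend on the arm. At 24 people, a few such decisions would matter.

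**Working it through.** **Sample size, as a check on inputs.** With d = 1.29, two-sided alpha 0.05 (sidedness is not stated; two-sided assumed) and 80% power, the two-sample t-test needs 10.49 per arm. That rounds to 11, or 22 in total, which matches the Sample section.

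**Does imbalance cost power?** The noncentrality is d × √(n₁n₂/(n₁+n₂)).
- 12:12: 1.29 × √(144/24) = 3.16, power 85.5%
- 13:11: 1.29 × √(143/24) = 3.15, power 85.3%
- 14:10: 1.29 × √(140/24) = 3.12, power 84.5%

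Power is not the issue.

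**Chance of missing 12/12.** Assumptions, since the documents give none: 24 people allocated one by one, strata equally likely, fixed permuted blocks.

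Blocks of 2 can be done by hand. A stratum of odd size leaves one unmatched person. As 24 is even, either no stratum or two strata are odd.
- 2 strata: P(both odd) = 1/2. The two leftovers share an arm with probability 1/2, so P(not 12/12) = 25%, half of it (12.5%) with HVB above 12.
- 3 strata: P(two odd) ≈ 3/4, so P(not 12/12) ≈ 3/4 × 1/2 = 37.5%, half of it (about 19%) with HVB above 12.

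Blocks of 4 were simulated.

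| Strata | Block size | Not 12/12 | HVB above 12 | Next arm certain |
|---|---|---|---|---|
| 2 | 2 | 25% | 12.5% | 48% |
| 2 | 4 | 37-38% | 19% | 30% |
| 3 | 2 | 37.5% | 19% | 47% |
| 3 | 4 | 50% | 25% | 28% |

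More strata and larger blocks make it worse: 4 strata with blocks of 6 miss 12/12 in 62% of runs. A single stratum, or strata whose sizes happen to be multiples of the block size, gives 12/12 with certainty.

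**Foreseeability (last column).** This assumes that block size, stratum and past assignments are all known. With blocks of 2, the second person in each complete block is certain.
- 2 strata: (1/2 × 12 + 1/2 × 11)/24 = 47.9%
- 3 strata: (1/4 × 12 + 3/4 × 11)/24 = 46.9%

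**Balance on IPPS.** SD of the between-arm difference in mean IPPS, in SD units, normal scores assumed:
- unmatched 12:12: √(1/12 + 1/12) = 0.41
- 2-3 strata, one by one: 0.21-0.26 (simulated)
- median split of a closed list of 24: √(1 − 2/π) × 0.41 ≈ 0.25
- 12 adjacent pairs of a closed list: about 0.09 (simulated), with 12/12 in every run.

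**The case against.** The strongest reply is that one-by-one allocation is an assumption. The plan describes one session per arm, which fits allocating everyone together, and pairing neighbours on IPPS is itself a form of 1:1 blocking on that score. A batch median split without ties at the cut would also give 12/12. This stands. A reader might infer that the planned method fails to deliver its arm sizes; the documents support only that nothing in them secures those sizes.

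A reader might also infer that the PI rules on eligibility and can foresee the arm. The documents say only that the PI receives enquiries and takes consent, and concealment is not described either way. The order of screening and IPPS completion is unclear too. If the ruling comes before the IPPS, the stratum is unknown, and the next arm is certain only when every stratum is forced to the same arm: about 12% (2 strata, blocks of 2), 5% (2 strata, blocks of 4) and 0.7% (3 strata, blocks of 4). Figures of 50% and 33% for blocks of 2 and 4 apply only when every block is complete.

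Finally, six per facilitator is called ideal, so a thirteenth HVB participant departs from a stated preference and breaks no fixed limit.

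What remains is that the choices deciding both matters are unstated, and a method that fits the session format does better on arm size, IPPS balance and foreseeability together.

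**Conclusion.** The point holds conditionally. Under one-by-one allocation with 2-3 strata and blocks of 2 or 4, the stated 12 per group is missed about a quarter to a half of the time, and HVB exceeds 12 about an eighth to a quarter of the time. The consequence is for session capacity, not power. Foreseeability is a real exposure only if block size, stratum and past assignments are known to someone who influences entry, and the documents neither show nor exclude that. If a batch draw was intended, the arm-size problem can disappear, but the text should say so. Even then, pairing balances IPPS clearly better than a median split (about 0.09 against 0.25 SD). The change is worth making before anyone is allocated.

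**What to change.** Replace the randomisation sentence in the Procedure section with wording such as:

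*Once consent, eligibility and IPPS are final for all participants and the baseline questionnaires are complete, the list is closed. Participants are ranked by IPPS (ties ordered at random), adjacent participants are paired, and one of each pair is assigned at random to HVB by an R script with a seed recorded in advance. The script is run once, by a team member not involved in recruitment. If the total is odd, the unpaired person is allocated by a simple random draw.*

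With 24 people this gives 12/12. With 23, the larger arm has 12, so HVB does not exceed 12 at allocation. No IPPS cut is needed, and no eligibility ruling follows the first assignment.

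In the Processing and Analysis Plan, add IPPS (or pair) as a covariate in the between-arm comparison; the planned unpaired tests ignore the matching and are usually conservative. For a t-type analysis of 24 people, an IPPS covariate leaves 24 − 3 = 21 residual degrees of freedom, against 12 − 1 = 11 for a fully paired analysis, so the covariate is the lighter choice.

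If the present scheme is kept, state the strata, block sizes, list holder, concealment and timing, and reconcile the possible arm sizes with the facilitator preference in the Sample section.

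The cost is a few sentences, a short script in software already planned, and an existing colleague to run it. The downsides are that participants learn their allocation only when the list closes, after the baseline questionnaires 7-10 days before the session, and that later withdrawals can still unbalance the arms.
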